For this trial we will treat for a maximum of 28 days. Our rationale for this timeframe is that while there is an expectation that the illness lasts up to 12-15 days in those who recover without complication, others will endure a longer duration, and some will experience persistent, new onset or worsening disease related symptoms. A recent study from the Centers for Disease Control and Prevention (https://www.cdc.gov/mmwr/volumes/70/wr/mm7017e3.htm?s cid=mm7017e3 w) found that among 3,171 non-hospitalized adult COVID-19 patients, 69% had one or more outpatient visits 28–180 days after the diagnosis. Two thirds had a visit for a new primary diagnosis, and approximately one third had a new specialist visit. Symptoms potentially related to COVID-19 were common new visit diagnoses. Visits for these symptoms decreased after 60 days but for some patients continued through 120–180 day. Furthermore, some individuals develop sequela that are likely related to post-viral immune dysregulation in the first few months albeit there is little known about this group. Though we are unlikely to learn about the effect of the drug in this latter population we do need to establish safety for a duration that includes the other groups mentioned above.

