3.2 Primary Endpoint

Incidence of Adverse Events and Serious Adverse Events assessed out to day 60.

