8.3 Analysis of Subject Disposition, History, and Baseline Characteristics

Subject disposition, including analysis population allocation, subjects enrolled, completed each period, discontinued, and primary reason for discontinuation, will be summarized using frequency and percentage. Protocol deviations will be summarized using frequency and percentage. Medical history data and prior and concomitant medications will be summarized using frequency and percentage. Subjects' age, height, weight, and baseline disease characteristics will be summarized using descriptive statistics. Gender, race, and other categorical variables will be provided using frequency and percentage.

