8.4 Safety & Tolerability Analyses

All safety & tolerability analyses will be performed on the Safety Population. The safety data will be presented in individual listings and summary tables.

Overall safety will be assessed by the number of belnacasan VX-765/RVT-201/MSR-001 dosed subjects experiencing a grade 4 or 5 SAE during the trial. Of 20 subjects enrolled in the belnacasan group, 3 or more developing a grade 4 or 5 SAE probably related to belnacasan would be

considered unlikely due to chance. Therefore, belnacasan will be determined safe if no more than

2 subjects develop a grade 4 or 5 SAE in the belnacasan group probably related to belnacasan.

In terms of stopping rules, should two or more subjects develop a similar Grade 3 SAE that is at

least possibly related to belnacasan or should one or more subjects develop a \geq Grade 4 SAE that

is at least possibly related to belnacasan, the trial will be paused for DSMB safety review.

Primary Endpoint Analysis

Primary endpoints of adverse and serious adverse events (AE/SAE) will be assessed by Poisson

regression for count data. Events will be counted out to 60 days from randomization to belnacasan

or placebo groups. Because some subjects may be followed for less than 60 days, subject follow-

up time will be included in the Poisson regression as the exposure time variable. If counts are not

Poisson-distributed, either over- or under-dispersed, negative binomial regression will be to

analyze AE/SAE events with appropriate adjustment for over/under dispersion. Comparison of

belnacasan vs. placebo will be expressed as the incidence rate ratio (IRR).

Adverse Events

AEs will be coded according to the latest version of the Medical Dictionary for Regulatory

Activities (MedDRA). The intensity/severity of AEs will be graded according to NCI-CTCAE (see

Section 7.3).

TEAEs, AEs leading to study treatment discontinuation, AEs leading to dose interruption, AEs

related to study medication, SAEs, and AEs leading to death will be summarized by system organ

class, preferred term, and study period. A summary of AEs that are CTCAE Grade 3 or higher, as

well as the most frequent preferred terms, will be provided.

If a subject experiences the same adverse events multiple times within a period, then the event will

be counted only once within the period and by greatest severity.

Descriptive statistics will be used to summarize the safety data.

Clinical Laboratory Values

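### The primary AE/SAE rate ratio runs to day 60 although dosing ends by day 28, and no rate ratio for the dosing window is planned, so on-drug harm is diluted

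*Combined protocol and SAP*

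**What the plan says.** Section 3.2 defines the primary endpoint as "Incidence of Adverse Events and Serious Adverse Events assessed out to day 60". Under Primary Endpoint Analysis, section 8.4 gives the model: "Primary endpoints of adverse and serious adverse events (AE/SAE) will be assessed by Poisson" regression, with negative binomial regression as the fallback if the counts are over- or under-dispersed. The window is explicit: "Events will be counted out to 60 days from randomization to belnacasan" or placebo. Each subject's follow-up time is the exposure variable, and the result is an incidence rate ratio (IRR).

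Section 1.3 sets the length of dosing: "For this trial we will treat for a maximum of 28 days". Section 5.3 expects that some subjects may want to stop well before that, because of minor side effects or because their symptoms have gone. Section 8.1 keeps them in the analysis while they remain consented.

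Section 7.6 promises separate summaries of events during treatment. Its definition of a treatment-emergent event has a start (the first dose) but no end. Sections 7.9 and 7.10 collect AEs until 28 days after the last dose. The schedule of events in 5.2 has AE assessments at days 42 and 60.

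Under a separate subheading, Adverse Events, section 8.4 describes tables: AEs "related to study medication, SAEs, and AEs leading to death will be summarized by system organ" class, preferred term and study period. The counting rule comes next. It concerns a subject who has the same event more than once in one period, and says that it is to "be counted only once within the period and by greatest severity". The word period is not defined there, nor in 8.3, which also uses it ("completed each period, discontinued, and primary reason for discontinuation").

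**The concern.** Safety is the primary objective, and the IRR is the only between-arm comparison planned for the primary endpoint. For a subject who completes dosing, more than half of the counted time (32 of 60 days) is time when a short-acting toxicity cannot show. Those days add similar numbers of events to both arms and pull the ratio toward 1. For a safety comparison, that is the direction that hides harm. With 20 subjects per arm there is little power to spare, and the result is meant to inform a larger trial.

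Two loose ends in the same text affect how the count is built. The once-per-period rule does not state its scope, and the AE collection window does not match the 60-day count.

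**Working it through.** **Inputs from the documents.** Dosing of at most 28 days (1.3); count to day 60 (3.2, 8.4); follow-up time as exposure (8.4); 20 subjects per arm and alpha 5% (8.7; sidedness is not stated, two-sided taken here).

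**Assumptions, not in the documents.** The drug doubles the AE rate while dosed and has no effect afterwards. The placebo AE rate and its time course are not given, so ranges are shown.

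**The plan's own figure.** Section 8.7 says that a difference in rate ratios of over 60% is needed for 80% power. Reading this as a ratio of 1.6, a Wald test on the log ratio needs ln(1.6)² × 20 × m / (1 + 1/1.6) = (1.96 + 0.84)² ≈ 7.85, so m ≈ 2.89 placebo events per subject. No base rate is stated, so the figure can be neither confirmed nor refuted; it is attainable. It does give a yardstick: a true doubling on drug exceeds 60%, but the diluted ratio below need not.

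**Step 1. Off-drug time.** 60 − 28 = 32 days for a subject who completes dosing, and more for one who stops early.

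**Step 2. Dilution at a constant background rate.** With d days of dosing, the 60-day IRR = (2d + 60 − d)/60.
- d = 28: 88/60 = 1.47
- d = 20: 80/60 = 1.33
- d = 14: 74/60 = 1.23

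If counting stops 28 days after the last dose, as in 7.9 and 7.10, a completer gives (56 + 28)/56 = 1.50.

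**Step 3. Dilution when events are not evenly spread.** If a share s of placebo-arm events falls in days 1-28 and all subjects complete dosing, the 60-day IRR = 1 + s.

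| s | 60-day IRR |
|---|---|
| 0.30 | 1.30 |
| 0.467 (constant rate) | 1.47 |
| 0.60 | 1.60 |
| 0.80 | 1.80 |

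**Step 4. Power.** Power = Φ(ln(IRR)/√(1/E0 + 1/E1) − 1.96), where E0 and E1 are the expected events in the placebo and belnacasan arms. There is no overdispersion and all subjects complete dosing.

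At 0.05 AEs per day and a constant rate:
- 60 days: E0 = 20 × 60 × 0.05 = 60, E1 = 88; 0.383/0.167 = 2.29; power 63%.
- Days 1-28: E0 = 20 × 28 × 0.05 = 28, E1 = 56; 0.693/0.231 = 2.99; power 85%.

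At other rates, and with early clustering:

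| Placebo events per subject in 60 days | Share in days 1-28 | Power, 60-day IRR | Power, 28-day IRR |
|---|---|---|---|
| 1 | 0.467 | 26% | 41% |
| 2 | 0.467 | 46% | 69% |
| 3 | 0.467 | 63% | 85% |
| 3 | 0.60 (E0, E1: 60, 96; 36, 72) | 81% | 92% |
| 3 | 0.80 (E0, E1: 60, 108; 48, 96) | 95% | 98% |

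The gain is large if AEs are spread evenly and small if most come early.

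**Step 5. What a dosing-window ratio recovers.** For completers, days 1-28 gives 2.0. If dosing lasts 20 days, days 1-28 gives (2 × 20 + 8)/28 = 1.71, against 1.33 over 60 days. A first-to-last-dose window gives 2.0 under these assumptions.

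**The case against.** Counting to day 60 is what the primary endpoint asks for. It captures late and delayed events and is a legitimate choice of target. No decision depends on the IRR: safety is declared from the number of belnacasan subjects with a probably related grade 4 or 5 SAE, and the pause rule uses possibly related SAEs. The protocol describes itself as hypothesis-generating and concedes limited power. All of this stands, and it keeps the point to a recommended addition.

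The constant-rate assumption is also open to challenge. Section 1.3 expects uncomplicated illness to last up to 12-15 days, so events may cluster early; Step 3 then gives 1.6 to 1.8. This stands too, and is why 1.47 is an illustration and not an estimate. The power figures would also fall with overdispersion, for which 8.4 makes provision.

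A first-to-last-dose ratio has its own weakness. Stopping because of intolerance or early recovery may be related to the outcome, and events just after the last dose are lost. That favours a fixed 28-day window by randomised arm.

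A reader might infer that the once-per-period rule contradicts the primary event count and attenuates the IRR further. Applied to the model, it would: with five preferred terms, 0.05 AEs per day and one 60-day period, each term has 0.60 expected placebo events and 0.88 on belnacasan, and (1 − e^−0.88)/(1 − e^−0.60) = 1.30. The documents do not support that reading. The rule stands under a different subheading, directly after the tables by preferred term and period. Its clause on greatest severity suits a tabulation and has no role in a count that ignores severity. What remains is missing detail: the scope is not stated and period is not defined.

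**Conclusion.** The primary IRR is less sensitive to harm during dosing than the data allow. If AEs double only on drug, it would read about 1.47 for completers at a constant background rate, 1.6 to 1.8 if 60 to 80% of placebo-arm events fall in days 1-28, and lower with early stopping (1.33 at 20 days of dosing). Power falls from about 85% to 63% at 0.05 AEs per day, and from 69% to 46% at 2 placebo events per subject in 60 days; with strong early clustering the loss is small. These sizes rest on an assumed doubling confined to dosing, assumed placebo rates and timing, and no overdispersion.

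This is a loss of sensitivity, not an error: the window agrees with the endpoint. Nor do the documents support saying that a doubling will read as 1.3 to 1.5. The upper end follows from the time split at a constant rate. The lower end needs early stopping, late-falling events or the counting rule applied to the model, and early clustering takes the ratio above that range.

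**What to change.** In section 8.4:

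1. Keep the 60-day IRR. Add an IRR from the same model for the dosing window: preferably days 1-28 by randomised arm, in all dosed subjects, with follow-up time within that window as exposure. Add a first-to-last-dose version, with days on drug as exposure, as a sensitivity analysis.
2. State that the once-per-period rule applies to the summary tables and not to the Poisson count. Define the periods, and say what counts as a new event in the model.
3. Reconcile AE collection in 7.9 and 7.10 (28 days after the last dose, about day 56 for a completer and day 48 for a subject who stops on day 20) with the count to day 60 and the day-60 AE assessment in 5.2. The exposure time should cover only days on which events were collected.

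The cost of items 1 and 2 is wording and one further model, plus its sensitivity version, on data already collected. The first-to-last-dose version carries a risk of informative truncation, which is why it should not be the main dosing-window result. Item 3 may need AE collection extended by a few days for completers and longer for early stoppers; alternatively the count window could be shortened, which would also change 3.2.

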1.4 Brief summary of known systemic safety profile of belnacasan (VX-765/RVT-201/MSR-001)

Based on files held by Vertex and Roivant Sciences, which contains evidence from animal and human studies, there is no indication that belnacasan (VX-765/RVT-201/MSR-001) causes severe or life-threatening side effects. The only preclinical finding on toxicity studies was a reduction of the heart rate in dogs at 2000mg/kg/day, a dose that was estimated to be 10-25 times higher than the maximum in this study (900mg QID). In humans with epilepsy the drug has been used at dosages of 3600mg/day for up to 13 weeks. Adverse effects reported in humans were headache, dizziness, nausea and vomiting, abdominal discomfort and rash. Seizure was reported in more than one patient in one study on epilepsy.

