5.2 Study Assessments

Table 1: Schedule of Events: **1** = In-Person; **2** = Telephone; **3** = Subject Self-Tracking

Time Point (Days)	Screen / enroll	D19	D4	D7	D10	D14	D21	D28	D42	D60	ET ¹⁰
STUDY TEAM											
Inclusion / Exclusion	İ										
Consent	İ							\			
Screening Tests ^{1, 12}	İ					1					
Demographics	İ										
CXR or CT ¹³	İ										
Physical Exam	İ			İ		1	Ť	Ţ			ţ
Vitals ²	İ			İ		İ	İ	İ			İ
EKG	İ			İ		İ	İ	İ			İ
CoV-2 N/P ³	İ					İ		Ť			Ť
Standard labs ^{4, 12}	İ			İ		Ì		Ť			Ť
Blood draws ^{5, 12}	İ			İ		1	Ť	Ť			İ
Immunology tests ^{6, 12}	İ			İ		Ì	Ť	Ť			Ť
CoV-2 blood ^{7, 12}								Ť			Ť
AE assessment	İ	2	2	İ	2	Ţ	İ	Ī	2	~	Ĭ
Symptoms assessment	İ	2	2	İ	2	Ţ	İ	İ	2	~	İ
WHO 9-Point Scale ⁸	İ	2	2	İ	2	Ţ	İ	İ	2	2	İ

SUBJECTS (as recorded in study diary)						
IP/placebo intake	Three times per day through day 28 or ET					
Temperature ¹¹	Daily via thermometer through day 28 or ET; subject will report via telephone to					
	study team at Day 42 & 60					
SpO2 resting ¹¹	Daily via pulse oximeter through day 28 or ET; subject will report via telephone to					
	study team at Day 42 & 60					
Symptom tracking	legistrian One time per day through day 28 or ET; subject will report via telephone to study					
	team at Day 42 & 60					

¹Screening tests: HIV, Hepatitis B, Hepatitis C, and pregnancy (serum pregnancy test for women of child-bearing potential per MedStar definition at enrollment and at day 14).

²Vital signs: oral temperature, heart rate, systolic blood pressure.

³Quantitative nasopharyngeal SARS-CoV-2 RNA testing (RT-PCR): nasopharyngeal or throat swabs will be used; any FDA-approved or commercial testing method will be acceptable. A home health agency may be used to confirm COVID-19 by RT-PCR in the subjects' home in the event their initial testing did not include PCR, to ensure expeditious resulting and appropriate inclusion into the trial. If home health is used to collect the PCR test or there is a delay in PCR resulting at initial screening, the subject will return to either MedStar Washington Hospital Center or MedStar Franklin Square for completion of the screening/enrollment visit in 1 to 3 days, once positive PCR is confirmed, to complete all study procedures including randomization and medication dosing under observation. ⁴Standard labs: serum chemistry, coagulation tests and hematology. Pregnancy tests for women of childbearing potential at screening, day 14 and end of treatment.

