5.3 Selection Criteria

Inclusion Criteria:

- Subject (or legally authorized representative) provides written informed consent prior to the initiation of any study procedures.
- Subject understands and agrees to comply with planned study procedures, including using the diary.
- Subject agrees to the collection of nasopharyngeal swabs and venous blood per protocol.
- Subject is male or non-pregnant female adult ≥18 years of age at time of consent.
 - Women with a history of menstruation must agree to use two methods of contraception, at least one of which is highly effective, for the duration of the study as well as to undergo additional pregnancy testing during the study.
- Subject has a laboratory confirmed SARS-CoV-2 infection as determined by RT-PCR assay prior to enrollment.
- Subject has evidence of either mild or moderate COVID-19 illness of less than 7 days from first onset, with minimal baseline symptom severity based on patient-reported FDA scoring system defined as follows:
 - Subject presents with at least two common symptoms of COVID-19 from the following list: stuffy or runny nose, sore throat, cough, low energy or tiredness, muscle or body ache,

⁶Immunology tests: COVID-19 relevant immunology labs (see Appendix 12.1 for complete list). See footnote to Appendix 12.1 as certain labs will be sent to and resulted from outside lab facilities.

⁷Quantitative blood SARS-CoV-2 antibody testing: Blood samples will be used; any FDA-approved or commercial testing method will be acceptable.

⁸WHO 9-point scale: see description of secondary end points for details.

headache, chills or shivering, feeling hot or feverish, nausea, vomiting, diarrhea, shortness of breath with exertion (without supplemental oxygen requirement) with a score of 2 or higher; impairment in sense of smell or taste with a score of 1 or higher **OR**

- Subject presents with any (i.e., at least one) symptom of COVID-19 as defined above AND clinical evidence of moderate COVID-19 as defined by FDA guidance for industry (such as respiratory rate >20 breaths per minute, heart rate >90 beats per minute, with oxygen saturation >93% on room air at sea level).
- Subject presents with high-risk for COVID-19-related inflammation determined by at least one comorbidity, including obesity, diabetes, hypertension, stable heart disease, respiratory disease, and / or non-severe fatty liver disease.

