All laboratory test results will be summarized by period together with the change from baseline.

The frequency distribution for low/normal/high or normal/abnormal will be summarized as well.

The denominators for calculating the percentages will be based on the number of subjects with

non-missing values in the Safety Population.

Vital Signs

Vital sign results will be summarized by period, together with the change from baseline.

Physical Examination

Summaries of physical examinations will present frequency distribution of abnormal findings by

body system and period. The denominators for calculating the percentages will be based on the

number of subjects evaluated for a particular body system of each dose level in the Safety

Population.

Electrocardiogram (EKG)

EKG findings will be classified as normal vs abnormal. The number and percentage of each

category will be summarized using frequency table for each period. The denominators for

calculating the percentages will be based on the number of subjects with non-missing values in

each period.

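### Section 8.4 counts normal and abnormal EKGs per period without comparing each subject with the enrollment EKG, so new or worsened findings cannot be read from the table

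*Combined protocol and SAP*

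**What the plan says.** The EKG paragraph in Section 8.4 has two working sentences. The first part reads "EKG findings will be classified as normal vs abnormal. The number and percentage of each" and the text continues "category will be summarized using frequency table for each period. The denominators for" the percentages, which are the subjects with non-missing values in that period. It provides no shift from enrollment, no grade of change, and no rate or interval.

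The neighbouring paragraphs of Section 8.4 treat other repeated safety measures differently:

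- Laboratory: "All laboratory test results will be summarized by period together with the change from baseline".
- Vital signs: "Vital sign results will be summarized by period, together with the change from baseline".

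As far as Table 1 in Section 5.2 can be read, EKGs are taken at screening/enrollment, on days 7, 14, 21 and 28, and at early termination. A baseline tracing therefore exists. The table's footnote defines vital signs as "oral temperature, heart rate, systolic blood pressure", at what appear to be the same visits.

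Section 5.3 requires "at least one comorbidity, including obesity, diabetes, hypertension, stable heart disease, respiratory disease" or non-severe fatty liver disease. On the cardiac side it excludes only heart disease that is uncontrolled and clinically significant. In Section 1.4, the animal toxicity summary states: "The only preclinical finding on toxicity studies was a reduction of the heart rate in dogs at 2000mg/kg/day".

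**The concern.** Safety and tolerability is the primary objective, and each subject who completes treatment contributes an enrollment EKG and four later ones. The question those tracings should answer is whether a subject's EKG changed after dosing, and whether that happened more often on belnacasan than on placebo. A percentage abnormal in each period does not answer it, for two reasons.

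- It gives the totals at each time but not the link between times. An abnormal count that stays level may be the same subjects throughout, or some who normalised and others who became abnormal.
- A subject who enters with an abnormal EKG and develops a further abnormality is counted the same way before and after.

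Both matter only if some subjects are abnormal at entry or move between categories. The eligibility criteria make that plausible without saying how often. The enrollment tracing that would resolve the matter is collected, but the stated analysis does not use it for any within-subject comparison.

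**Working it through.** The plan gives no EKG figure to reproduce, so the check is how much the planned table leaves undetermined.

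**Inputs**

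- n = 20 subjects per arm (Section 8.7).
- b = number abnormal at enrollment and f = number abnormal at a later visit. Both are assumed, because the documents give no entry rate; the values below run from 2 to 12 of 20.
- All 20 subjects are assumed to have a readable EKG at both times. Missing tracings would widen the ranges, since each period has its own denominator.

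**Formulas**

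Subjects abnormal later are either new (normal at enrollment) or abnormal at both times.

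- New abnormalities cannot be fewer than the net rise: lower bound = max(0, f − b).
- They cannot exceed the number abnormal later or the number normal at entry: upper bound = min(f, n − b).
- Subjects abnormal at both times, any of whom may have worsened without altering the table, number at most min(b, f).

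**Results per arm**

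| b | f | New abnormal EKGs compatible with the table | Abnormal at both times, at most |
|---|---|---|---|
| 2 | 2 | 0 to 2 | 2 |
| 4 | 4 | 0 to 4 | 4 |
| 6 | 6 | 0 to 6 | 6 |
| 8 | 8 | 0 to 8 | 8 |
| 10 | 10 | 0 to 10 | 10 |
| 6 | 8 | 2 to 8 | 6 |
| 10 | 12 | 2 to 10 | 10 |

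Worked example for b = f = 6: the lower bound is max(0, 6 − 6) = 0 and the upper bound is min(6, 20 − 6) = min(6, 14) = 6. For b = 6, f = 8: max(0, 8 − 6) = 2 and min(8, 14) = 8.

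**What this means between arms.** If both arms show 6 abnormal at enrollment and 6 later, their tables are identical. Yet one arm could hold 0 new abnormalities and the other 6, a difference of 6 of 20 subjects.

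**What a plain shift table would do.** Cross-classifying normal/abnormal at enrollment against normal/abnormal later fixes the number of new abnormalities exactly. It still does not show worsening among subjects abnormal at both times. That needs a judgement of change against the enrollment tracing, or numeric change from enrollment.

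**The case against.** The strongest defence is that the cardiac effect named in Section 1.4 is already monitored. The finding is a slower heart rate. Heart rate is one of the vital signs, and Section 8.4 summarizes vital signs with change from baseline. This stands in full. A reader might infer that the trial could neither show nor exclude the one preclinical signal; the documents do not support that. The dog finding also arose at a dose that Section 1.4 estimates at 10 to 25 times the maximum it names, which limits its weight, and no interval or conduction signal is reported in animals or humans. Intervals are therefore worth adding as ordinary EKG description, and cannot be presented as following from that finding.

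Second, individual cases need not be lost. Section 7.6 counts a pre-existing condition that worsens as treatment-emergent, Section 7.9 defines an adverse event to include any unfavorable sign, and Section 8.4 provides subject listings. This stands for single cases that an investigator recognises and records. It does not supply a systematic comparison of EKGs with enrollment by arm.

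Third, a reader might infer that a chance imbalance at entry would pass for a drug effect. That goes too far. The term period is not defined, and if enrollment is one of the tabulated periods, the imbalance would be visible beside the later percentages.

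Fourth, it is tempting to say that abnormal EKGs at entry will be common. The comorbidity requirement can be met by obesity, diabetes or fatty liver disease alone, and uncontrolled heart disease is excluded. The documents support only that some subjects may be abnormal at entry.

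Last, the EKG summary is descriptive in a 40-subject proof-of-concept trial. Power for a test of percentage abnormal would be beside the point, because no such test is planned. That keeps the point small but leaves the missing comparison in place.

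**Conclusion.** The point holds in a limited form. The EKG analysis as written cannot identify new abnormalities and conceals worsening in subjects already abnormal, although the enrollment EKG is scheduled and the same section uses baseline for laboratory results and vital signs. The gap concerns rhythm, conduction and other EKG findings; heart rate is covered elsewhere.

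Its size depends on an entry rate that the documents do not give. With 20 evaluable subjects per arm and between 2 and 10 abnormal at both times, the table fits anything from 0 up to 2 to 10 new abnormal EKGs. If nobody is abnormal at entry, b = 0 and both bounds equal f, so the count of new abnormalities at each later visit is exact. The problem therefore exists only to the extent that abnormal EKGs are present at enrollment.

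This is a minor refinement of a descriptive safety table. It does not affect the primary adverse event comparison or the safety decision rule.

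**What to change.** In the EKG paragraph of Section 8.4:

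- Classify each post-dose EKG against the subject's own enrollment EKG as new or worse, or as unchanged or improved, and tabulate number and percentage by arm and visit. Use as denominator the subjects with an EKG at both enrollment and that visit.
- Where the EKG printout gives intervals, report their change from enrollment descriptively by arm and visit.
- State whether period means visit, and whether enrollment is one of the tabulated periods.

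No model is needed. Section 8.4 says safety data are summarized descriptively, and the mixed models in Section 8.5 are for the secondary treatment-effect endpoints, with no baseline adjustment stated.

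The cost is a few CRF fields, a reading of each tracing beside the enrollment one, and one more descriptive table. No additional EKG is required and no clinical rule changes.
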